12.1 General Considerations

Data analysis will be performed using SAS® Version 9.2 or higher.

Data listings will be provided for all data collected as required by this protocol, ordered by actual exposure and subject and time point (if applicable), unless otherwise stated. Summary statistics and statistical analysis will only be presented for data where detailed in this SAP. All unscheduled assessments will be included in the listings.

Safety data will be summarized for the Safety Population, biomarker data will be summarized and analyzed for the FAS unless otherwise stated.

12.1.1 Stratified Presentation

Primary BoExp summaries will be produced by arm, sex (male and female), CC consumption (10-19 CC/day vs. >19 CC/day) and time point (if applicable), unless otherwise stated.

12.1.2 Subgroup Analyses

No subgroup analyses will be performed in this study.

12.1.3 Descriptive Statistics

For continuous data, summary statistics will include the number of subjects (n), the number and percent of subjects with missing data, the arithmetic mean, arithmetic SD, median, first and third quartiles, minimum, maximum, and number; for log-normal data the geometric mean and geometric CV will also be presented. For categorical data, frequency counts and percentages will be presented. Data listings will include all subject level data collected unless otherwise specified. Summary statistics and statistical analyses will generally only be performed for subjects included in the relevant analysis population. For the calculation of summary statistics and statistical analysis, unrounded data will be used.

Summaries on the Safety Population will be produced by actual exposure, including the additional set of subjects who tested the product but were not enrolled or were discontinued from enrolment before randomization.

The following product labels will be used throughout the TFLs (**Table 17**):

Table 17: Product Labels

Product	Format used in TFLs	Order in TFLs
Tobacco Heating System 2.2	THS 2.2	1
Conventional cigarettes	CC	2
Smoking abstinence	SA	3

The following stratification labels (Table 18) for the TFLs will be used:

Table 18: Stratification Labels

Stratification Factor	Definition
Sex	male
	female
Daily CC consumption (per day)	<10 ¹
	10-19
	>19

¹ Note that due to inclusion criteria for the study there should not be any subjects with ISO nicotine level > 1.0 mg, therefore this category will not be presented unless there is sufficient data for analysis/presentation (see Section 12.1.5.1 "Insufficient Data for Analysis/Presentation").

12.1.4 Definitions for Statistical Data Analysis

The following definitions (Table 19) for statistical analyses/presentations will be used:

Table 19: Definition of terms for the statistical analysis

Term	Definition
Baseline Value	The last assessment prior to 06:29 AM on Day 1

N.B. For data where baseline is different to the above will be defined in the specific section of the SAP.

For urine collections taken on Days x to y, e.g., Days 5 to 6, these will be referred to as collected on Day x, i.e., Day 5, in the SAP.

12.1.5 Handling of Dropouts or Missing Data (including outside the limits of quantification)

In general, missing data will not be imputed in this study, due to the nature of the measurements and the short periods of exposure and use. However, for questionnaire data total scores and domain or subscale scores may use a certain degree of imputation (by averaging across individual item scores) as detailed in Section 7.3 "Questionnaires".

Laboratory parameters will be presented as detailed in Section 7.1 "Biomarkers".

12.1.5.1 Insufficient Data for Analysis/Presentation

If there are no values/events at the general value then the break out should not be presented. For example if the number of related AEs is zero then no presentation by severity of related events at the single level will be produced.

Some of the TFLs will not have sufficient numbers of subjects or data for presentation. If this occurs, the blank TFL shell will be presented with a message printed in the center of the table, such as, "No serious adverse events occurred for this study."

For categories of summaries that have <4 subjects no summaries will be shown.

12.1.6 Handling of Unplanned Data

Unscheduled post-product use readings will be excluded from the summary statistics. Unscheduled readings will be labelled as unscheduled in the listings and mapped to the study day using the date of the study day until midnight.

12.1.7 Multiple Comparisons / Multiplicity

The primary endpoints will be tested using a multiple testing procedure to preserve the overall alpha level by simultaneously testing the endpoints using a closed procedure with each test performed at an alpha level of 5%. This implies that statistical significance is required for all primary endpoints in order to be able to make confirmatory claims about any of the endpoints.

No adjustment will be made on any of the secondary endpoints.

12.2 Disposition of Subjects

The number and percent of subjects will be summarized for the following categories: subjects screened, screening failures that tried product, screening failures that did not try product, enrolled subjects, enrolled and not randomized, randomized subjects, completed, and discontinued (if applicable discontinued subject that never used their allocated products will be identified).

Subjects in the Safety Population will be displayed by actual exposure.

Inclusion and exclusion criteria will be listed as to whether the subjects have met or not met the criteria.

All subjects who fail to complete the study will be categorized by their primary reason for discontinuation and summarized by actual exposure. Disposition of subjects and reasons for withdrawal will also be summarized separately. Supportive listings will be provided.

The number and percent of randomized subjects with protocol deviations and the number of protocol deviations will be summarized by actual exposure, broken down by main deviation category (major/minor) and sub-categories. Subjects will be counted once per deviation category, and can be counted for more than one deviation category.

Supportive listing will be provided, including any additional comments for tests that are not performed to be included on the listings of individual data.

The data will be presented in the below outputs, the TFL number refers to the TFL number in the accompanying TFL shell document:

TFL number	Title
TABLES	
15.2.1.1	Summary of Subject Disposition – All Screened Subjects
15.2.1.2	Summary of Reasons for Discontinuations – All Randomized Subjects
15.2.1.3	Summary of Protocol Deviations – Safety Population
LISTINGS	
15.3.1.1	Listing of Inclusion/Exclusion Criteria
15.3.1.10	Listing of Subject Disposition, Randomization and Assignment to Analysis Sets
15.3.1.13	Listing of Protocol Deviations
15.3.2.7	Listing of Subject and Observations Excluded from Efficacy Analysis
16.1.7	Listing of Randomization Schemes and Codes

12.3 Demographics and Other Baseline Characteristics

Demographic and baseline characteristics will be summarized for the Safety Population and FAS, and listed for all screened subjects.

The demographic variables age, sex, race, body weight, height and BMI will be summarized by actual exposure, and by the two stratification factors (sex, and CC consumption). Other baseline characteristics will also be included in the table.

No inferential analyses will be presented for the demographic and baseline characteristics.

The data will be presented in the below outputs, the TFL number refers to the TFL number in the accompanying TFL shell document:

TFL number	Title
TABLES	
15.2.1.4.1	Summary of Demographics and Other Baseline Characteristics – Safety Population
15.2.1.4.2	Summary of Demographics and Other Baseline Characteristics – FAS
15.2.1.4.2.1	Summary of Demographics and Other Baseline Characteristics by Sex – FAS
15.2.1.4.2.2	Summary of Demographics and Other Baseline Characteristics by Cigarette Consumption – FAS
LISTINGS	
15.3.1.9	Listing of Demographics

12.3.1 FTND Questionnaire at Screening

FTND score value and the number and percentage of subjects in each category (mild/moderate/severe) will be presented. Data will be listed and summarized as reported in Section 12.3 “Demographics and Other Baseline Characteristics”.

The data will be presented in the below outputs, the TFL number refers to the TFL number in the accompanying TFL shell document:

TFL number	Title
TABLES	
15.2.1.4.1	Summary of Demographics and Other Baseline Characteristics – Safety Population
15.2.1.4.2	Summary of Demographics and Other Baseline Characteristics – FAS
15.2.1.4.2.1	Summary of Demographics and Other Baseline Characteristics by Sex – FAS
15.2.1.4.2.2	Summary of Demographics and Other Baseline Characteristics by Cigarette Consumption – FAS
LISTINGS	
15.3.1.12	Listing of Fagerström Test for Nicotine Dependence Results

12.3.2 Current Cigarette Brand and Smoking Characteristics

The following smoking characteristics at Admission (Day -2) will be summarized and listed as specified in Section 12.3 “Demographics and Other Baseline Characteristics”. ISO tar yields (continuous and categorized as 1-5 mg, 6-8 mg, 9-10 mg and > 10 mg), ISO nicotine level (continuous and categorized as \leq 0.6 mg and > 0.6 to \leq 1 mg), and number of CCs smoked on a daily basis during the previous 4 weeks (continuous and categorized as 10-19 CC/day and >19 CC/day).

Current CC brand(s) smoked by the subject and recorded at the Screening Visit and Admission (Day -2) will be summarized and listed by actual exposure and study day for the Safety Population. This will include brand name(s) and ISO nicotine, tar, and CO yields. Data at screening will be listed only.

Smoking history, including whether subjects have smoked for at least the last three consecutive years and whether the subject smoked any mentholated CCs during the previous 4 weeks will be listed by actual exposure at Screening and Admission (Day -2) where applicable. Responses to planning to quit smoking during the next 3 months will be listed at Screening. Readiness to accept interruption of smoking for up to 5 days and the advice on the risks of smoking and debriefing will be listed at Admission.

Data will be listed and summarized as presented in the below outputs, the TFL number refers to the TFL number in the accompanying TFL shell document:

TFL number	Title
TABLES	
15.2.1.4.1	Summary of Demographics and Other Baseline Characteristics – Safety Population
15.2.1.4.2	Summary of Demographics and Other Baseline Characteristics – FAS
15.2.1.4.2.1	Summary of Demographics and Other Baseline Characteristics by Sex – FAS
15.2.1.4.2.2	Summary of Demographics and Other Baseline Characteristics by Cigarette Consumption – FAS
15.2.1.5	Summary of Current Cigarette Brands – Safety Population
LISTINGS	
15.3.1.2	Listing of Current Cigarette Brands
15.3.1.3	Listing of Smoking History
15.3.1.5	Listing of Advice on Risks of Smoking
15.3.1.6	Listing of Willingness to Abstain from Smoking During the Next 3 Months
15.3.1.7	Listing of readiness to Accept Interruption of Smoking for up to 5 days

12.3.3 Medical History and Concomitant Diseases

Medical history is defined as any condition that started and ended prior to Screening. Medical history will be coded using MedDRA version 16.0 and listed separately by actual exposure, System Organ Class (SOC) and Preferred Term (PT) within SOC.

Medical History will be summarized by actual exposure, SOC and PT for the FAS.

Concomitant disease is defined as any condition diagnosed at Screening or was ongoing at Screening. Concomitant disease will be coded using MedDRA version 16.0 and listed separately by actual exposure, SOC and PT within SOC.

Concomitant disease will be summarized by actual exposure, SOC and PT for the Safety Population.

Partial dates will not be imputed, but assumptions will be made as follows to assign to either medical history or concomitant diseases:

Date information	Assign as
Missing stop date	Concomitant disease
Partial date, e.g. --May2012, or ----2011. If month/year is the same as, or later than the month and/or year of Screening.	Concomitant disease
Partial date, e.g. --May2012, or ----2011. If month and/or year is earlier than the month and/or year of Screening.	Medical history

The data will be presented in the below outputs, the TFL number refers to the TFL number in the accompanying TFL shell document:

TFL number	Title
TABLES	
15.2.1.6	Summary of Medical History – Safety Population
15.2.1.7	Summary of Concomitant Diseases – Safety Population
LISTINGS	
15.3.1.11	Listing of Medical History and Concomitant Diseases

12.3.4 Other Data

Other data collected at Screening and/or Admission will be listed by actual exposure. These data are as follows:

- Cotinine urine test
- Urine pregnancy test
- Chest x-ray
- Urine drug screen
- Serology
- Alcohol breath test
- Prior medication
- Debriefing and risk of smoking
- Willingness to use THS 2.2

Willingness and ability to use the products will also be summarized.

The data will be presented in the below outputs, the TFL number refers to the TFL number in the accompanying TFL shell document:

TFL number	Title
TABLES	
15.2.6.10.1	Summary of Prior Medication by Anatomical Therapeutic Classes (ATC) 1 and 2 – Safety Population
15.2.6.10.2	Summary of Prior Medication by Preferred Term – Safety Population
LISTINGS	
15.3.1.4	Listing of Product Test and Willingness to Use the Product
15.3.1.8	Listing of Safety Laboratory Entry Criteria
15.3.6.3	Listing of Prior and Concomitant Medication

12.4 Measurements of Product Compliance

During the confinement period, compliance to product/regimen allocation (exclusive use of THS 2.2 and CC in THS 2.2 and CC arms, respectively, and full abstinence from smoking in the SA arm) will be ensured by strict distribution of each Tobacco Stick/CC when requested by the subject.

In addition, levels of CO in exhaled breath will be measured in the SA arm to ensure that the subjects have not smoked any cigarettes. This will serve as a compliance tool during the confinement period. These data (continuous and categorical) will be summarized and listed by actual exposure.

The data will be presented in the below outputs, the TFL number refers to the TFL number in the accompanying TFL shell document:

TFL number	Title
TABLES	
15.2.5.1	Summary of Compliance as Measured by Exhaled CO (ppm) in the SA Arm- Safety Population
LISTINGS	
15.3.3.2	Listing of Secondary Biomarkers and Sampling/Collection Times

12.5 Extent of Exposure (Product Consumption)

Details of the product test prior to enrolment and of daily product use after randomization will be listed and summarized.

The data will be presented in the below outputs, the TFL number refers to the TFL number in the accompanying TFL shell document:

TFL number	Title
TABLES	
15.2.2.1	Summary of Use of THS 2.2 Product and CC – Safety Population
LISTINGS	
15.3.2.1	Listing of Product Usage
15.3.2.2	Listing of Cigarette Butt and THS Tobacco Stick Collection Data

12.6 Planned Statistical Analyses

Markedly non-lognormally distributed BoExp data will be transformed or analyzed by appropriate non-parametric methods with bootstrapping using the SAS procedure PROC SURVEYSELECT. The seed to be used in any analysis will be contained in the SAS output and will be different for each analysis.

For all statistical analysis data from all arms, THS 2.2, CC and SA will be included in all models.

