**Table 16. Coefficients of Variation (YVD-CS01-EU study)**

| | THS 2.2 /CC MR (CV) | THS 2.2 /SA MR (CV) |
|--------|------------------------|------------------------|
| COHb | 0.40 (0.32) | 2.10 (0.20) |
| 3-HPMA | 0.30 (0.50) | 1.70 (0.33) |
| MHBMA | 0.15 (0.70) | 1.00 (0.35) |
| S-PMA | 0.20 (0.70) | 1.15 (0.42) |

Abbreviations: 3-HPMA = 3-hydroxypropylmercapturic acid; CC = conventional cigarettes; COHb = carboxyhemoglobin; CV = coefficients of variation; MHBMA = monohydroxybutenyl mercapturic acid; MR = mean ratios; S-PMA = S-phenylmercapturic acid; SA = smoking abstinence; THS 2.2 = Tobacco Heating System 2.2.

Table 17 describes the expected coefficients of variation (CV) and mean ratios (MR) between THS 2.2 and the CC control arm based on data from a single-center, open-label, randomized, controlled, 2-arm parallel group study to evaluate the exposure to selected smoke constituents in smoking, but otherwise healthy subjects switching from conventional cigarettes to THS 2.1 compared to subjects continuing to smoke CC for 5 days, the ZRHX-EX-01 study (ClinicalTrials.gov: ID: NCT01780714) sponsored by PMI.

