**Table 17. Coefficients of Variation (ZRHX-EX-01 study)**

| | THS 2.2 /CC MR (CV) |
|--------|------------------------|
| COHb | 0.44 (0.14) |
| 3-HPMA | 0.28 (0.20) |
| MHBMA | 0.11 (0.47) |
| S-PMA | 0.07 (0.50) |

Abbreviations: 3-HPMA = 3-hydroxypropylmercapturic acid; CC = conventional cigarettes; COHb = carboxyhemoglobin; CV = coefficients of variation; MHBMA = monohydroxybutenyl mercaptyuric acid; MR = mean ratios; S-PMA = S-phenylmercapturic acid; THS 2.2 = Tobacco Heating System 2.2.

Based on these two sets of assumptions, the power to demonstrate a reduction was computed. Table 18 describes the expected power to demonstrate a reduction on 4 primary BoExps in smokers switching from CC to THS 2.2 as compared to those continuing to smoke CC, using one-sided test with 2.5% type I error probability using the assumptions from YVD-CS01-EU and ZRHX-EX-01 and 160 smokers (80 in THS 2.2, 40 in CC, and 40 in the SA arm).

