**Table 18. Expected power (YVD-CS01-EU and ZRHX-EX-01 studies assumptions)**

| Assumptions | Reduction | | | | | |
|-------------|-----------|------|-----|-----|-----|-----|
| | 50% | 51% | 52% | 53% | 54% | 55% |
| YVD-CS01-EU | 96% | 91% | 85% | 75% | 63% | 48% |
| ZRHX-EX-01 | >99% | >99% | 96% | 81% | 48% | 16% |

A total of 160 smokers (80 in THS 2.2, 40 in CC, and 40 in the SA arm) will be randomized to demonstrate to demonstrate a reduction of at least 50% on 4 primary BoExps in smokers switching from CC to THS 2.2 as compared to those continuing to smoke CC, using one-sided test with 2.5% type I error probability.

Power considerations related to secondary endpoints of biological changes:

The sample size is sufficient to obtain 95% CIs for the ratio between (geometrical) mean levels of primary BoExps in THS 2.2 and SA see Section 12.2 with upper and lower limits deviating not more than 18% from the point estimates, with an 80% overall probability of achieving the desired precision of estimating the true mean.

This study has 80% power using a one-sided test with 2.5% type I error probability:

- To detect a 0.631 [ml/min/kg] (29%) difference between THS 2.2 and CC in CYP1A2 activity, as measured by the CAF clearance, assuming a standard deviation of 0.564. Effect size and variability are derived from data obtained in the YVD-CS01-EU study sponsored by PMI.
- To detect a 24.71 [ng/g creatinine] (20%) difference between THS 2.2 and CC in 11-DTX-B2, assuming a standard deviation of 43.78, as reported by Saareks et al, 2001. The anticipated effect size of THS 2.2 is assumed to be about 90% of the effect of smoking cessation reported in the paper by Saareks et al, 2001.

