8 SAMPLE SIZE JUSTIFICATION

The following discussion addresses the ability to demonstrate on Day 5 a reduction of at least 50% on four selected primary BoExp in smokers switching from CC to THS 2.2 as compared to smokers continuing to smoke CC.

Table 11 describes the expected coefficients of variation (CV) and mean ratios (MR) between THS 2.2 and the two control arms in COHb, 3-HPMA, MHBMA and S-PMA on Day 5 based on data from a controlled, randomized, open-label, 3-arm parallel single-center confinement study that investigated exposure to selected smoke constituents in smokers switching from CCs to smoking article (SMAR) cigarettes for 5 days, the YVD-CS01-EU study (ClinicalTrials.gov: ID: NCT00812279) sponsored by PMI. The mean ratios and CVs for SMAR/CC are expected to be the same as THS 2.2/CC.

Table 11: Coefficients of Variation (YVD-CS01-EU study)

	THS 2.2 /CC MR (CV)	THS 2.2 /SA MR (CV)
COHb	0.40 (0.32)	2.10 (0.20)
3-HPMA	0.30 (0.50)	1.70 (0.33)
MHBMA	0.15 (0.70)	1.00 (0.35)
S-PMA	0.20 (0.70)	1.15 (0.42)

Abbreviations: 3-HPMA = 3-hydroxypropylmercapturic acid; CC = conventional cigarettes; COHb = carboxyhemoglobin; CV = coefficient of variation; MHBMA = monohydroxybutenyl mercaptyuric acid; MR = mean ratio; S-PMA = S-phenylmercapturic acid; SA = smoking abstinence; THS 2.2 = Tobacco Heating System 2.2.

Table 12 describes the expected CV and MR between THS 2.2 and the CC control arm in COHb, 3-HPMA, MHBMA, S-PMA based on data from a single-center, open-label, randomized, controlled, 2-arm parallel group study to evaluate the exposure to selected smoke constituents in smoking, apparently healthy subjects switching from CC to THS 2.1 compared to subjects continuing to smoke CC for 5 days, the ZRHX-EX-01 study (ClinicalTrials.gov: ID: NCT01780714) sponsored by PMI. The mean ratios and coefficients of variations for THS 2.1/CC are expected to be the same as THS 2.2/CC.

Table 12: Coefficients of Variation (ZRHX-EX-01 study)

	THS 2.2 /CC MR (CV)
COHb	0.44 (0.14)
3-HPMA	0.28 (0.20)
MHBMA	0.11 (0.47)
S-PMA	0.07 (0.50)

Abbreviations: 3-HPMA = 3-hydroxypropylmercapturic acid; CC = conventional cigarettes; COHb = carboxyhemoglobin; CV = coefficients of variation; MHBMA = monohydroxybutenyl mercaptyuric acid; MR = mean ratios; S-PMA = S-phenylmercapturic acid; THS 2.2 = Tobacco Heating System 2.2.

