**Table 13: Expected Power (YVD-CS01-EU and ZRHX-EX-01 Studies Assumptions)**

Assumptions	Reduction					
	50%	51%	52%	53%	54%	55%
YVD-CS01-EU	96%	91%	85%	75%	63%	48%
ZRHX-EX-01	>99%	>99%	96%	81%	48%	16%

A total of 160 smokers (80 in THS 2.2, 40 in CC, and 40 in the SA arm) will be randomized to demonstrate a reduction of at least 50% on 4 primary BoExp in smokers switching from CC to THS 2.2 as compared to those continuing to smoke CC, using one-sided test with 2.5% type I error probability.

The sample size is sufficient to obtain 95% CIs for the ratio between (geometrical) mean levels of primary BoExp in THS 2.2 and SA with upper and lower limits deviating not more than 18% from the point estimates, with an 80% overall probability of achieving the desired precision of estimating the true mean.

This study has 80% power using a one-sided test with 2.5% type I error probability:

1. To detect a 0.631 [mL/min/kg] (29%) difference between THS 2.2 and CC in CYP1A2 activity, as measured by the CAF clearance, assuming a standard deviation (SD) of 0.564. Effect size and variability are derived from data obtained in the YVD-CS01-EU study sponsored by PMI.
2. To detect a 24.71 [ng/g creatinine] (20%) difference between THS 2.2 and CC in 11-DTX-B2, assuming a SD of 43.78. The anticipated effect size of THS 2.2 is assumed to be about 90% of the effect of smoking cessation.

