12.6.2 Secondary Analyses

12.6.2.1 Biomarkers of Exposure

In addition, the quantity excreted over 24 hours for MHBMA, 3-HPMA and S-PMA will be presented.

The primary BoExp will also be examined to compare the reductions in THS 2.2 vs. SA using the same methodology as for the primary analysis.

The secondary BoExp are exhaled CO, total 1-OHP in urine, total NNN in urine, 4-ABP in urine, 1-NA in urine, 2-NA in urine, o-tol in urine, CEMA in urine, HEMA in urine, B[a]P in urine, HMPMA in urine, S-BMA in urine, total NNAL in urine and NEQ in urine. The urine parameters will be expressed as concentrations adjusted for creatinine and the quantity excreted over 24 hours.

The baseline of the exhaled CO will be the time-matched measurements on Day 0, i.e. the 1st measurement on Days 1 to 5 will be matched to the 1st measurement on Day 0 and similarly for the 2nd, 3rd and 4th measurements. The baseline of the urinary biomarkers will be the last assessment prior to 06:29 AM on Day 1.

The values and percent changes for urinary BoExp in the quantity excreted over 24-hours and the concentration adjusted for creatinine will be listed and summarized. In addition line graphs will be produced for product means (and 95% CI) over all timepoints.

CO in exhaled breath will be measured using the Micro+™ Smokerlyzer® or similar device, conducted on Day -2 to Day 6. On Day -1 to Day 5 the first test per day will be performed within 15 minutes prior to the first product use and then between 12:00 and

02:00 PM, between 04:00 and 06:00 PM and between 08:00 and 10:00 PM. On Days -2 and Day 6 the CO breath tests will be conducted once.

Descriptive statistics summarized by exposure will be produced separately for all timepoints for all visits applicable for exhaled CO. This will be done on the FAS, stratified by sex, and CC consumption.

Actual values and percent changes from baseline in levels of exhaled CO will be listed and summarized. In addition line graphs will be produced for product means (and 95% CI) over all timepoints.

The last measurement of exhaled CO will be used in the analysis. An ANCOVA model will be used with terms for the baseline value, sex, average daily CC consumption over the last 4 weeks as reported during screening and product. No adjustment will be made for multiple comparisons.

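### The primary ANCOVA fits one residual variance to all three arms, the sample-size section rests on two, and no action is set for unequal variances

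*SAP*

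**What the plan says.** SAP 12.6 sets the data for every model: "For all statistical analysis data from all arms, THS 2.2, CC and SA will be included in all models". The PROC MIXED code in SAP 12.6.1.1 regresses log Day 5 on log baseline, sex, cigarette consumption and product. It has no REPEATED statement with a GROUP option, so there is a single residual variance. SAP 12.6.2.1 then says the primary biomarkers will be examined to "compare the reductions in THS 2.2 vs. SA using the same methodology as for the primary analysis".

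The sample-size section (Protocol 12.2, SAP 8) tabulates a mean ratio and a CV for each contrast from YVD-CS01-EU. The COHb row reads "COHb | 0.40 (0.32) | 2.10 (0.20" and the S-PMA row "S-PMA | 0.20 (0.70) | 1.15 (0.42", with THS 2.2/CC first and THS 2.2/SA second. SAP 8 carries these over: "The mean ratios and CVs for SMAR/CC are expected to be the same as THS 2.2/CC". Two planning claims follow: the joint power row in Protocol Table 18, "YVD-CS01-EU | 96% | 91% | 85% | 75% | 63% | 48", and 95% CIs for THS 2.2:SA with "upper and lower limits deviating not more than 18% from the point estimates", at 80% overall probability.

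Protocol 12.4.4 says the model assumptions will be tested, and the SAP does not withdraw this. In both documents the only stated action is for markedly non-lognormal data.

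**The concern.** If one residual variance held in all three arms, the two CV columns would agree. They differ for every primary endpoint: 0.32 against 0.20, 0.50 against 0.33, 0.70 against 0.35, and 0.70 against 0.42 (COHb, 3-HPMA, MHBMA, S-PMA). The analysis model therefore does not match the plan's own assumptions.

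With 2:1:1 allocation, ANCOVA loses the protection that equal arm sizes give against unequal variances. All four biomarkers must show the 50% reduction. COHb decides this, with a planned ratio of 0.40–0.44, while the other three lie at 0.07–0.30. An error in the COHb standard error passes almost directly into the study's one-sided 2.5%. For THS 2.2:SA, pooling in a more variable arm would widen the interval beyond the planned precision.

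**Working it through.** **Inputs.** CVs and ratios from Protocol Table 16; 80/40/40 subjects; one-sided 2.5%; margin 0.50. Log-scale variance v = ln(1+CV²). For COHb this is 0.0975 (THS 2.2/CC) and 0.0392 (THS 2.2/SA). For S-PMA it is 0.3988 and 0.1625. The factor 1/80 + 1/40 = 0.0375.

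**1. Power row.** For each endpoint, take a noncentral t with 118 df and noncentrality ln((1−R)/MR)/√(0.0375·v), with R the reduction to be shown, and multiply over the four endpoints.

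| Reduction | 50% | 51% | 52% | 53% | 54% | 55% |
|---|---|---|---|---|---|---|
| Stated | 96 | 91 | 85 | 75 | 63 | 48 |
| THS 2.2/CC CVs | 95.5 | 91.4 | 84.8 | 75.2 | 62.8 | 48.5 |

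The THS 2.2/SA CVs would give 86% in the last cell. COHb alone drives the row (95.55% of the 95.5% at 50%).

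**2. Precision claim.** The 80th percentile of the upper deviation is exp(t·√(v·0.0375)·√(χ²₀.₈/118)) − 1, with t = 1.980 and √(χ²₀.₈/118) = 1.052.

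| | COHb | 3-HPMA | MHBMA | S-PMA |
|---|---|---|---|---|
| THS 2.2/SA CVs | 8.3% | 13.9% | 14.7% | 17.7% |
| THS 2.2/CC CVs | 13.4% | 21.0% | 29.0% | 29.0% |

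Only the first row meets 18%. The two planning claims use different variances.

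**3. COHb error at a true ratio of 0.50, no baseline effect.** The model uses v̄ = (2v_THS + v_CC + v_SA)/4 and SE_model = √(0.0375·v̄). The true value is SE_true = √(v_THS/80 + v_CC/40). Error ≈ 1 − Φ(1.96·SE_model/SE_true). The documents give no arm variances, so the splits are assumptions. In the last three rows each CV is read as pooled over two arms with THS 2.2 weight w, and v_THS = v_SA = 0.0392, so v_CC = (0.0975 − w·0.0392)/(1−w).

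| Split | v_CC | v̄ | SE_model | SE_true | Error |
|---|---|---|---|---|---|
| All equal, 0.0975 | 0.0975 | 0.0975 | 0.0605 | 0.0605 | 2.5% |
| Only SA lower (v_THS = v_CC) | 0.0975 | 0.0829 | 0.0558 | 0.0605 | 3.5% |
| w = 1/3 | 0.1266 | 0.0611 | 0.0479 | 0.0605 | 6.0% |
| w = 1/2 | 0.1558 | 0.0684 | 0.0506 | 0.0662 | 6.7% |
| w = 2/3 | 0.2140 | 0.0829 | 0.0558 | 0.0764 | 7.6% |

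**4. With baseline adjustment.** The SAP ANCOVA was simulated (40,000 trials per case; when the CC baseline–Day 5 correlation is above 0, THS 2.2 has 0.5 and SA 0.3).

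- Only SA less variable: 3.5, 3.2, 2.4, 2.0 and 1.5% at CC correlations 0, 0.5, 0.7, 0.8 and 0.9. At high correlation CC has the smaller residual variance after adjustment, and the common variance overstates the standard error.
- The three w splits: 6.1, 6.6 and 7.5% at correlation 0, and 3.5, 4.1 and 5.3% at 0.9.
- A second simulation gave 3.7% falling to 1.5% when only SA is less variable, and 4.4%–8.0% when CC is also noisier.
- Arm-specific variances gave 2.3%–2.7%. A Bartlett test at 5% with a switch to arm-specific variances when significant gave 2.3%–2.9%.

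**5. THS 2.2:SA precision for S-PMA under the SAP model.** Use the step 2 formula with v̄ and 154 df (t = 1.975, factor 1.046). Only SA lower: v̄ = (3·0.3988 + 0.1625)/4 = 0.3397, giving 26.3%. The pooled splits with v_THS = v_SA = 0.1625 give v̄ = 0.2806 and 23.6% at w = 1/2, and v̄ = 0.3397 and 26.3% at w = 2/3. At w = 1/3, v̄ = 0.2511 and the figure is 22.2%. These assume no baseline effect. In simulation with CC correlation 0.7–0.9 the figure falls to about 19%–22%, and in the most favourable split to 17.8%.

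**The case against.** **The Protocol already tests assumptions.** Protocol 12.4.4 covers equal variances, and a test followed by a switch controls the error well. This stands in part. What is missing is the test, its level and the consequence, so the choice would be made after the data are seen.

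**No arm variance is given.** This stands, and it limits the claim. A reader might infer from Table 16 that the CC arm is noisier than the THS 2.2 arm, and so that the primary test runs at 5%–8%. The documents do not support that. The CV entry is not defined: it could be a two-arm pooled value, a control-arm value or a baseline-adjusted residual. The power row itself reproduces with one SD for THS 2.2 and CC. The CVs come from another product, and the nearer predecessor study, ZRHX-EX-01 ("COHb | 0.44 (0.14"), has no SA column. What the two columns indicate is that SA is less variable than CC.

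**The sign is not settled.** This stands. CC subjects keep smoking their own brand, so a high baseline–Day 5 correlation is plausible. If only SA is less variable, the planned test is then conservative. If the CVs are already baseline-adjusted, the zero-correlation figures apply instead.

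**The decision rule is inferred.** SAP 12.6.1.2 writes the null as no reduction, while SAP 5.5.2 requires 50%. Comparing the upper limit with 0.50 is my reading; the power row reproduces on that basis.

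**THS 2.2:SA is descriptive.** This stands. The error there is towards wider intervals: simulated COHb coverage without a baseline effect was 98.0%–100%.

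**Conclusion.** The mismatch is certain: one residual variance in the model, two in the sample-size section, and no stated consequence if variances differ. The effect is conditional. For COHb at a true ratio of 0.50, one-sided error is about 1.5%–3.7% if only SA is less variable, and at or below 2.5% at high CC correlation. It is about 4%–8% if CC is also noisier than THS 2.2, which needs the pooled reading of the CVs. That second range is a possibility to guard against and not a finding about this trial. For S-PMA, THS 2.2:SA limits would deviate by about 24%–27% in most splits without a baseline effect, and about 19%–22% with strong correlation, against 18% stated.

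**What to change.** Before unblinding, allow arm-specific residual variances in the SAP 12.6.1.1 code, for example `repeated / group=product;` with `ddfm=kr` on the MODEL statement. Take the THS 2.2:CC and THS 2.2:SA 95% CIs from that model, and report the common-variance ANCOVA as a sensitivity analysis. Alternatively, keep the common-variance model as primary and pre-specify the variance test, its level and the switch to arm-specific variances. Removing SA from the model is not enough: under the pooled reading with 2:1 weights, a two-arm common variance still gives 4.9%–7.6%.

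The cost is two lines of SAS and matching SAP text, with no extra subjects. If all variances are equal, joint power under the YVD-CS01-EU assumptions falls from 95.4% to 95.1%. If CC is noisier, the THS 2.2:CC interval widens. Over eight assumed splits with no baseline effect, joint power was 80.8%–95.5%. One added extreme split (w = 2/3, THS 2.2 variance half of SA) gave 78.0%, just under the 80% target.
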